2.3. Benefit/Risk Assessment

More detailed information about the known and expected benefits and risks and reasonably expected AEs of PF-07304814 may be found in the latest IB (December, 2020), which is the SRSD for this study.

Potential for increased risk of intravenous infusion site reaction.	There may be potential risk of infusion site reaction due to low pH of study intervention and/or need for continuous intravenous infusion. - These risks are described in the SRSD for PF-07304814.	Monitoring of infusion site reactions will be performed through targeted PE and collection of AEs, which will be reviewed on an ongoing basis. Infusion solution may be diluted.
Other		
Not applicable.		

2.3.2. Benefit Assessment

Since this is the first clinical study of PF-07304814 the clinical benefit is unknown. The phosphate prodrug PF-07304814 is not expected to be active against the SARS 3CL protease. PF-00835231 (active moiety) has been shown to have SARS-CoV-2 antiviral activity in vitro, and it is intended to reduce virus titers and thereby reduce disease severity and risk of mortality in SARS-CoV-2 infected patients. Participants in this study therefore have the potential to benefit from PF-07304814 administration, however the benefit is unproven.

2.3.3. Overall Benefit/Risk Conclusion

Taking into account the measures to minimize risk to participants in this study, the potential risks identified in association with PF-07304814 are justified by the potential anticipated benefits that may be afforded to hospitalized participants with SARS-CoV-2 infection.

3. OBJECTIVES, ESTIMANDS, AND ENDPOINTS

Objectives	Estimands	Endpoints
Primary:	Primary:	Primary:

To assess the safety and tolerability following single and multiple ascending doses of PF-07304814 in hospitalized participants with COVID-19.	N/A	
Frequency, severity, and causal relationship of TEAEs and withdrawals due to TEAEs (including infusion site reactions).Frequency and magnitude of abnormal laboratory findings.Changes from baseline in vital sign measurements, pulse oximetry/SpO₂, and 12-lead ECG parameters.
Secondary:	Secondary:	Secondary:

To evaluate the plasma PK of PF-07304814 and PF-00835231 and urinary PK of PF-00835231 following single ascending and multiple ascending doses in hospitalized participants with COVID-19.	N/A	Part 1: SAD 
PF-07304814 (prodrug) and PF-00835231 (active moiety) plasma PK: C₂₄ (end of infusion) and C₂₄ (dn).PF-00835231 urinary PK parameters: Ae, Ae%. Part 2: MAD 
PF-07304814 (prodrug) and PF-00835231 (active moiety) plasma PK: C₁₂₀ (end of infusion), C_{max}, C_{ss}, and t_{1/2}.
Tertiary/Exploratory:	Tertiary/Exploratory:	Tertiary/Exploratory:
■ [REDACTED]	C CI	■ [REDACTED]

Measurement of	N/A	
SARS-CoV-2 viral load (RT-PCR) and, if

Objectives	Estimands	Endpoints
SARS-CoV-2 viral load (by RT-PCR) and, if feasible, molecular analysis in nasopharyngeal swab and saliva samples over time.		feasible, molecular analysis in nasopharyngeal swab and saliva (at Screening, Days 1, 2, 3 and 6 for Part 1: SAD , and at Screening, Days 1, 3, 6, 7, 10, 14 and last follow-up for Part 2: MAD).

 Measurement of exploratory biomarkers. 	N/A	
 Change from baseline in biomarkers (on Days 1, 2, 3 and 6 for Part 1: SAD, and Days 1, 3, 6, 7, 10, 14 and last follow-up for Part 2: MAD may include: 
 Cytokines of inflammatory response (eg, IL-1B, IL-2, IL-4, IL-6, IL-8, IL-10, IL-12p70, IL-13, TNF-α, and IFN-γ); Coagulation (eg, PT, aPTT, D-dimer), fibrinogen and haptoglobin; Generalized endothelial damage/anemia (eg, ferritin); Cardiac dysfunction (eg, CK, proBNPII, and troponin); General markers of sepsis/organ damage (eg, LDH, hsCRP, and cystatin-C), procalcitonin; Serological endpoints: anti-SARS CoV-2; 
C C I

C
 
CI
		
C
 
CI

C
		

4. STUDY DESIGN

4.1. Overall Design

This is a First-In-Human Phase 1b study to evaluate the safety, tolerability and PK of PF-07304814 in participants who are hospitalized for treatment of COVID-19. The participants will be receiving SoC therapy for the treatment of mild, moderate, or severe COVID-19, but will not be eligible if they require mechanical ventilation or ECMO at screening or baseline. All participants will have a confirmed positive test for SARS-CoV-2 (see [Section 5.1](#) for additional details) and onset of symptoms within 15 days of Screening. For inclusion into **Part 2: MAD** of the study, participants will be required to have had a positive test for SARS-CoV-2 (See [Section 5.1](#) for details) within 72 hours prior to Screening.

This is a 2-part study in which up to a total of approximately 72 participants on SoC with the intervention such that approximately 72 evaluable participants complete the study. It is a randomized, double-blind, sponsor-open, parallel group, placebo-controlled trial.

Part 1: SAD is to evaluate safety, tolerability, and PK of escalating doses of PF-07304814 given as 24-hour IV infusions. Two planned and 3 optional cohorts with 8 participants/cohort will be included in **Part 1**. **Part 2: MAD** is to evaluate safety, tolerability, and PK of multiple ascending doses of PF-07304814 given as 120-hour IV infusions. Two planned and 2 optional cohorts with 8 participants/cohort will be included in **Part 2**.

4.1.1. Part 1: SAD

Precautionary **sentinel** dosing will be used in each dose-escalating, ie, increasing dose, cohort in **Part 1**. A small cohort of 2 participants (1 receiving PF-07304814 and 1 receiving placebo) will be dosed prior to the remainder of the cohort. All available safety and tolerability data from the 2 sentinel participants up to at least Day 3 at 24 hours post completion of dosing will be reviewed by the Investigator(s) (if available), the study team and IRC. The independent IRC will then determine whether it is safe to proceed to dose the remaining participants in the cohort.

Cohorts of 8 participants each who meet the eligibility criteria (see [Sections 5.1](#) and [5.2](#)) will be enrolled. The 2 sentinel participants will be randomized in a ratio of 1 (PF-07304814): 1 (placebo), while the remaining 6 participants will be randomized in a ratio of 5 (PF-07304814):1 (placebo). Both treatments will be administered in a telemetered (for 12 hours post the start of dosing) setting as a continuous IV infusion for 24 hours for each dose, in addition to SoC therapy.

All participants will follow the study procedures as outlined in [Section 1.3, SoA](#). They will be required to stay in hospital from at a minimum, Day 1, pre-dose (at least 2 hours) through completion of Day 3 evaluations (Follow-up 1). Participants will then return for Day 6 (Follow-up 2) activities and a planned final follow-up visit per the [SoA](#) on Day 30-37 (Follow-up 3) for a total of approximately 4-5 weeks study participation from first dose to follow-up, excluding screening.

Participants who discontinue for reasons other than drug-related safety events during the trial may be replaced at the discretion of the Sponsor and investigator.

Three optional cohorts may be added to further explore the dose range based on emerging safety, tolerability and PK assessments. However, the projected exposures at the top dose (adjusted based on observed PK) in **Part 1: SAD** will not exceed the exposure limits agreed with competent regulatory authorities.

After reviewing emerging safety, tolerability, and PK data ([Section 6.6.1](#)) by the study team, the Investigator(s) (if available) and IRC, the decision to proceed to the next dose level will be made.

4.1.2. Part 2: MAD

Progression to **Part 2** will occur if safety, tolerability, and PK data from the **Part 1** 24-h infusion cohorts as well as those from study C4611007 are determined to be supportive and acceptable by competent regulatory authorities. The dose progression will be based on emerging PK, safety and tolerability data and will not exceed the exposure limits agreed with competent authorities.

Cohorts of 8 participants each who meet the eligibility criteria (see [Sections 5.1](#) and [5.2](#)) will be enrolled and randomized in a ratio of 6 PF-07304814:2 placebo. All participants will follow the study procedures as outlined in [SoA](#). They will be required to stay in hospital from at a minimum, Day 1, pre-dose through completion of Day 7 evaluations (Follow-up 1). Participants will then return for Day 10 (Follow-up 2) and Day 14 (Follow-up 3) activities and a final planned follow-up (Follow-up 4) visit per the [SoA](#) on Days 34-41 for a total of approximately 5-6 weeks study participation from the start of dosing to follow-up, excluding screening.

Participants who discontinue for reasons other than drug-related safety events during the trial may be replaced at the discretion of the Sponsor and investigator.

4.2. Scientific Rationale for Study Design

This study will provide data on safety, tolerability, PK, biomarker changes and measures of disease activity in hospitalized patients infected with SARS-CoV-2. Since this is a first in human study, patients who require mechanical ventilation or suffer from severe, uncontrolled co-morbidities will be excluded to balance potential risk versus benefit. Risk is further mitigated by a single dose escalation design in **Part 1: SAD**, with extensive assessment of safety and PK. Precautionary sentinel dosing will also be used in each dose-escalating cohort in **Part 1**. A small cohort of 2 participants (1 receiving PF-07304814 and 1 receiving placebo) will be dosed prior to the remainder of the cohort. An independent IRC will assess whether it is safe to proceed to continued dosing within a cohort following sentinel dosing or whether it is safe to dose-escalate to the next dose level. In **Part 2**, PF-07304814 will be administered for a period of 5 days of continuous infusion at a dose based on emerging data and with the agreement of the competent regulatory authority. The potential for PF-07304814

to have beneficial antiviral activity will be explored by measurement of viral load, biomarkers of disease and assessment of disease progression on **CCI**

The clinical benefit of PF-07304814 is unproven, and therefore to ensure all participants get the best care for COVID-19 study intervention will be administered in addition to SoC.

Studies to evaluate the development toxicity of PF-07304814 have not been conducted. Therefore, the use of a highly effective method of contraception is required (see [Appendix 4: Contraceptive Guidance](#)).

In addition to clinical safety and PK data, biofluids will be collected for virology and PD exploratory biomarker assessments at various times per schedule of assessments. In brief, nasopharyngeal swab and saliva samples will be collected for viral load assessments, and where feasible, viral genetic analysis. Emerging reports have suggested that COVID-19 patients can exhibit abnormal innate and adaptive immune responses to SARS CoV-2 infection.²⁰ As a result, immunological biomarkers (eg, monocyte profiles, interferon gamma, C-reactive protein, tumor necrosis factor, IL-6 and IL-8) will be assessed in blood. Serological endpoints will be examined as well. Literature reports also suggest a significant percentage of patients exhibit endothelial dysfunction and coagulation and specific organ vulnerabilities.^{21,22} Blood will also be collected to examine coagulation endpoints (eg, D-dimer, and ferritin) and other specific organ damage endpoints (eg, cardiac troponin, etc).

CCI

4.3. Justification for Dose

Doses presented are projected based on nonclinical data and may be modified based on emerging safety, tolerability, and PK data.

4.3.1. Rationale for Dose Selection

The approach for dose selection for this study includes consideration of all relevant information obtained in non-clinical pharmacology and toxicity studies with PF-07304814 or PF-00835231 (active moiety). Similar to other antiviral therapies, PF-00835231, the active moiety of the phosphate prodrug PF-07304814, is expected to exhibit therapeutic anti-SARS-CoV-2 activity in patients when the free plasma exposure is maintained at or above the in vitro EC₉₀ values.²³⁻²⁵

4.3.2. Starting Dose and Dose Escalation in Part 1: SAD

This is a study in COVID-19 patients who are on SoC. To maximize the potential benefit of an anti-viral agent, the planned starting dose of PF-07304814 is to maintain a free plasma concentrations (C_{ss}) of PF-00835231 (active moiety) around EC₉₀ of 0.5 μM (or a total plasma concentration of 0.526 μg/mL) according to in vitro pharmacology studies ([Section 2.2.1.2.2](#)).

Based on the predicted human PK parameters (Section 2.2.1.2.1), at a dose of 500 mg of PF-07304814 administered over 24-hour as a continuous infusion, the projected PF-00835231 (active moiety) C_{ss} is 0.53 $\mu\text{g}/\text{mL}$ and the AUC_{24} is 11.2 $\mu\text{g}\cdot\text{h}/\text{mL}$. CCI

[REDACTED] (Section 2.2.1.3). At this dose, the projected PF-07304814 exposures (C_{ss} and AUC_{24}) provide at least 2.5-fold safety margins relative to the PK stopping limits (Section 2.2.1.3).

As of 18 November 2020, 4 patient participants received a single dose of 500 mg PF-07304814 or placebo administered as a 24-hour continuous IV infusion in study C4611001. While the preliminary safety profiles were acceptable, the exposures achieved at 500 mg in C4611001 were ~2-fold of initial PK stopping limits based on preliminary results in a limited number of patients who received active treatment. As such, the enrolment to Cohort 1 at 500 mg was stopped and a new cohort (Cohort 3) at 250 mg is open to enrolment.

If dose progression is further explored in Part 1 of the study, the predicted exposures for both PF-00835231 and PF-07304814 will not exceed the agreed PK stopping limit with competent regulatory authorities.

4.3.3. Starting Dose and Dose Selection in Part 2: MAD

The starting dose of Part 2 is determined to be 5 daily doses of 250 mg via continuous infusion after careful review of all available safety and PK data from Part 1: SAD of study C4611001 as well as data from study C4611007. This starting dose has been selected to balance the safety of trial participants while maintaining the $C_{ss} > EC_{90}$ through the entire dosing interval and is intended not to exceed the initial PK stopping limits, CCI [REDACTED] (Table 5).

Emerging PK data from those who received active treatment of 500 mg in Part 1 suggest that the exposures (C_{max} and AUC) of the active moiety PF-00835231 were roughly 2-fold (AUC_{24}) to 3-fold (C_{max}) higher compared to those observed in healthy participants (C4611007) based on geometric mean values. The $t_{1/2}$ was similar to those in healthy participants when values could be calculated.

Because of the anticipated higher exposure in the patient population as compared to healthy participants and the variability in patients observed so far, 250 mg daily for 5 days dosing regimen will enhance the probability of maintaining the $C_{ss} > EC_{90}$ for patients enrolled. Therefore, this starting dosing regimen will balance achieving antiviral activity while remaining within the initial PK stopping limits CCI [REDACTED]

If the 250 mg daily for 5 days dosing regimen is safe and well tolerated, further dose escalation will be guided by safety as well as PK of the drug. The escalation increment, if explored will be $\leq 2.5X$ (eg, from 250 mg to ≤ 625 mg). Two optional cohorts may be added to explore higher doses or to repeat a dose to expand the cohort. Dose escalation will only proceed after gaining agreement on the dose level from competent regulatory authorities.

Furthermore, dose escalations will be undertaken in a cautious manner such that systemic exposures of PF-00835231 and PF-07304814 at any dose level in Part 2 will not exceed exposure observed from mid-dose of CCI [REDACTED] (Section 2.2.1.3).

Projected PK exposure parameters and safety margins of PF-00835231 and PF-07304814 relative to exposure limits for **Part 2** based on initial PK stopping limits at the planned dose are listed in Table 5 and Table 6, respectively. Doses presented are projected based on preliminary PK results from study C4611007.

Table 5. Predicted Human Plasma Total Exposure and Safety Margins of PF-00835231 Relative to Exposure Limits at Planned Dose Levels

Dose (mg)	C _{max} (μ g/mL)	AUC ₂₄ (h* μ g/mL)	AUC _{inf} (h* μ g/mL)	C _{max} ^a safety margin	AUC ₂₄ ^b safety margin	AUC _{inf} ^b safety margin
^c 250 x 5	0.545	12.7	NA	2.8	2.2	NA

c. Predicted based on emerging preliminary PK from study C4611007 assuming linear kinetics; C_{max} and AUC₂₄ on Day 5 listed. However, limited emerging PK data from those who received active treatment of 500 mg in Part 1 suggest that the exposures (C_{max} and AUC) of the active moiety PF-00835231 were roughly 2-fold (AUC₂₄) to 3-fold (C_{max}) higher compared to those observed in healthy participants (C4611007) based on geometric mean values.

Table 6. Predicted Human Exposure and Safety Margins of PF-07304814 Relative to Exposure Limits at Planned Dose Levels

Dose (mg)	C _{max} (μ g/mL)	AUC ₂₄ (h* μ g/mL)	AUC _{inf} (h* μ g/mL)	C _{max} ^a safety margin	AUC ₂₄ ^b safety margin	AUC _{inf} ^b safety margin
^c 250 x 5	0.230	3.72	NA	3.6	4.1	NA

c. Predicted based on emerging preliminary PK from study C4611007 assuming linear kinetics; C_{max} and AUC₂₄ on Day 5 listed.

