2.2.2. Clinical Overview

C4611001 is the first clinical study using PF-07304814, and is designed to establish PK, safety and tolerability in a hospitalized COVID-19 population. In order to evaluate these parameters in a more homogeneous healthy population, an additional Phase 1 study, C4611007, is initiated and ongoing. Following the establishment of PK, safety and

tolerability of 24h and 120h infusions of PF-07304814 in these populations, the sponsor proposes a Phase 2/3 adaptive design efficacy study in hospitalized COVID-19 patients (C4611002).

As of 18 November, 2020, 4 patient participants in Cohort 1 received a single dose of PF-07304814 or placebo, administered as a 24-hour continuous IV infusion in the study C4611001. Based on emerging PK data in participants who received PF-07304814, dosing in Cohort 1 (500 mg dose) was stopped and dosing in a new cohort, Cohort 3, at 250 mg was initiated. As of 16 December, 2020, three participants in Cohort 3 have been dosed with either PF-07304814 or placebo.

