Maximum or near maximum plasma concentrations of the active moiety PF-00835231 were generally first observed ~6h post start of the infusion and sustained until the end of the infusion. PF-00835231 plasma concentrations declined rapidly afterwards. The $t_{1/2}$ values were only reportable at 500 and 700 mg and were 2.25 hour and 2.02 hour, respectively. Mean C_{max} and AUC values appeared to increase in a dose proportional manner in the dose range tested.

Maximum or near maximum plasma concentrations of the phosphate prodrug PF-07304814 were generally first observed ~3h and sustained until at least 16h post start of the infusion. Despite continuous infusion of the prodrug and sustained plasma concentration of the active moiety, the concentration of PF-07304814 declined before the end of the infusion. The $t_{1/2}$ values could not be determined since all plasma samples collected after the 16h post start of the infusion were BLQs of 40 ng/mL. While the mean C_{max} values appeared to increase in a dose proportional manner in the dose range tested, the AUC values appeared to increase in a slightly greater than dose proportional manner.

More detailed information may be found in the latest IB (December, 2020).

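### Table 5's margins for the Part 2 starting dose (2.8 and 2.2) are healthy-participant margins; with the protocol's own patient ratios the active-moiety margins are about 0.9 (Cmax) and 1.1 (AUC24)

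*Protocol*

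**What the plan says.** Section 4.3.3 sets the Part 2 starting dose at 250 mg daily for 5 days by continuous infusion. It describes the dose as "intended not to exceed the initial PK stopping limits", cites Table 5, and concludes that "this starting dosing regimen will balance achieving antiviral activity while remaining within the initial PK stopping limits".

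Table 5 gives one row for PF-00835231 (the active moiety) at this dose: Cmax 0.545 µg/mL with margin 2.8, and AUC24 12.7 h·µg/mL with margin 2.2, both for Day 5. Footnote c states the source: "Predicted based on emerging preliminary PK from study C4611007 assuming linear kinetics". Section 2.2.2.1 identifies C4611007 as the healthy-participant study.

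Footnote c then turns to "limited emerging PK data from those who received active treatment of 500 mg in Part 1" and reports active-moiety exposures roughly 2-fold (AUC24) to 3-fold (Cmax) above those in healthy participants, on geometric means. Section 4.3.3 gives the same ratios in its text. Section 4.3.2 adds that "the exposures achieved at 500 mg in C4611001 were ~2-fold of initial PK stopping limits". Section 2.2.2 records the response: "dosing in Cohort 1 (500 mg dose) was stopped and dosing in a new cohort, Cohort 3, at 250 mg was initiated".

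The numerical limits are in Section 6.6.1, listed for Part 1: total Cmax 1.53 µg/mL and total AUC24 28.2 µg·h/mL for PF-00835231, applied to average exposure.

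**The concern.** The conclusion in Section 4.3.3 is about patients, while the margins it cites are for healthy participants. The protocol reports a difference in exposure between the two populations that is about as large as the margins themselves, yet neither the margins nor the conclusion was changed.

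The two halves of the conclusion also rest on different populations. The antiviral half relies on patients: "Because of the anticipated higher exposure in the patient population as compared to healthy participants" introduces the argument that the regimen will help keep steady-state concentration above EC90. The only visible margins for the safety half are the healthy-participant ones.

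Table 5 is the visible quantitative margin for the first 120-hour infusion in patients. An ethics or safety reviewer would read a margin above 2 differently from one of about 1.

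**Working it through.** **Inputs**
- Limits, PF-00835231 total plasma (Section 6.6.1): Cmax 1.53 µg/mL, AUC24 28.2 µg·h/mL.
- Healthy-participant projection, 250 mg/day, Day 5 (Table 5): Cmax 0.545, AUC24 12.7.
- Patient-to-healthy ratios (Section 4.3.3 and footnote c): about 2 for AUC24, about 3 for Cmax.
- Patient exposure at 500 mg (Section 4.3.2): about 2 times the initial limits.

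**1. Reproduce Table 5.** Margin = limit / projected exposure.
- Cmax: 1.53 / 0.545 = 2.81, printed as 2.8.
- AUC24: 28.2 / 12.7 = 2.22, printed as 2.2.

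The divisions are right, and they show that the Section 6.6.1 limits are the ones used.

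**2. Scale to patients.** Patient exposure = ratio × healthy exposure.
- AUC24: 2 × 12.7 = 25.4; 28.2 / 25.4 = 1.11; 25.4 / 28.2 = 90% of the limit.
- Cmax: 3 × 0.545 = 1.635; 1.53 / 1.635 = 0.94; 1.635 / 1.53 = 107% of the limit.

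**3. Second route.** About 2 times the limits at 500 mg × 250/500 = about 1.0 times the limits. This assumes proportionality in patients and uses the same patients, so it checks consistency and adds no new evidence. Section 4.3.2 does not say which parameter or analyte the 2-fold refers to.

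**4. Which row agrees with the 500 mg observation?** Doubling each row to 500 mg:
- Healthy row: 2 × 12.7 / 28.2 = 0.90 and 2 × 0.545 / 1.53 = 0.71 times the limits.
- Patient-scaled row: 2 × 25.4 / 28.2 = 1.80 and 2 × 1.635 / 1.53 = 2.14 times the limits.

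Only the patient-scaled row fits the reported figure of about 2.

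**5. Does the 3-fold Cmax ratio carry over to Day 5?** The healthy row is nearly flat: 0.545 / (12.7/24) = 1.03 peak to average. The scaled row gives 1.635 / (25.4/24) = 1.54, which is peaked for a continuous infusion. If Day 5 is flat in patients and only the 2-fold ratio applies (an assumption; the protocol ties 3-fold to Cmax), Cmax is 2 × 0.545 = 1.09 and the margin 1.53 / 1.09 = 1.40.

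**6. Rounding.** The protocol says roughly; ±0.5 on each figure is an assumption.

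| Quantity | Assumed range | Margin |
|---|---|---|
| AUC24 ratio | 1.5 to 2.5 | 1.48 to 0.89 |
| Cmax ratio | 2.5 to 3.5 | 1.12 to 0.80 |
| 500 mg multiple of limits | 1.5 to 2.5 | 1.33 to 0.80 |

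Every range includes 1, and none reaches 2.2 or 2.8.

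**7. Number of patients.** Four participants had received 500 mg or placebo. Under Section 4.1.1 the sentinel pair contributes one active; the next two, from a 5:1 allocation, contribute one or two. The ratios therefore rest on 2 or 3 active patients.

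**The case against.** The case for leaving the text alone is substantial.

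- **Nothing is miscalculated or hidden.** Table 5 names its source, and footnote c gives the ratios and the parameter each belongs to. This stands. What remains is that the reader has to do a division that removes most of the margin, and that the conclusion does not reflect it.
- **The conclusion is not shown to be false.** AUC24 alone stays inside the limit at 90%. Cmax exceeds it by about 7%, on very few patients and a rounded ratio. This also stands: the figures neither confirm nor refute that patients would remain within the limits.
- **Not all of the justification is visible.** Text next to both statements about the limits is redacted, and Table 5 footnotes a and b cannot be read. Patients were already being dosed at 250 mg in Cohort 3, with no PK shown. The point can therefore address only the visible statement.
- **Linearity in patients is untested in the visible text.** Section 2.2.2.1 reports that "AUC values appeared to increase in a dose proportional manner in the dose range tested", but for healthy participants.
- **The consequence is contained.** The numerical limits are stopping rules for Part 1. Progression to Part 2 required regulators to accept the Part 1 data, and later escalation needs patient PK through 120 h and agreement with authorities. Exposure in Part 2 is capped at that of a nonclinical mid-dose. If that is 360 mg/kg/day (an inference from Section 2.2.1.3), its free Cmax of 3.92 µg/mL and AUC24 of 71.9 µg·h/mL are about 5.8 times the initial free limits (3.92/0.67 and 71.9/12.4). This lowers the stakes, but Section 4.3.3 itself chose to measure the starting dose against the initial limits.

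A reader might infer that the sponsor knowingly started Part 2 above its limits, or that a stopping rule was met. The documents support neither: the projection straddles 1, and the average-exposure rule is not stated for Part 2.

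**Conclusion.** The point holds as a mismatch between a justification and the population it is applied to; it is not an arithmetic error. For PF-00835231 at 250 mg/day for 5 days, the protocol's own ratios turn the printed margins of 2.8 (Cmax) and 2.2 (AUC24) into about 0.94 and 1.11. The visible claim that the regimen remains within the initial limits is therefore not supported by the margins offered for it; the supportable statement is that expected mean patient exposure is at about those limits.

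This rests on ratios from 2 or 3 active patients, on their rounding, and on a linear carry-over from 500 mg over 24 h to Day 5 at 250 mg. It covers the active moiety only: no patient ratio is given for the prodrug, so Table 6 cannot be rescaled. No breach is proven and no change of dose follows.

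**What to change.** Add a patient-scaled row for PF-00835231 to Table 5: AUC24 25.4 h·µg/mL (margin 1.1) and Cmax 1.64 µg/mL (margin 0.9). Note beneath it that the row rests on 2 or 3 active patients, rounded ratios and an assumed linear carry-over from 500 mg over 24 h to Day 5 at 250 mg. State separately, labelled as an assumption, that Cmax would be about 1.09 µg/mL (margin 1.4) if Day 5 is flat and only the 2-fold ratio applies.

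Reword the Section 4.3.3 conclusion to say that expected mean patient exposure is at about the initial PK stopping limits.

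The cost is one table row, one note and one sentence. It needs no new data and no change to dose, endpoints or analysis. The downside is a less favourable stated margin.
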